3 METHODS AND DESIGN

This trial is a randomised controlled parallel-group trial with three intervention arms and one control arm. The primary purpose is to assess the effects of three different types of dietary recommendations for reducing free sugars, on free sugar intakes over 12 weeks, in individuals consuming >5% TEI from free sugars. Secondary aims will investigate how these different recommendations affect secondary outcomes, outcomes in subsets of the trial population, and will identify potential barriers and facilitators to dietary change.

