5.1.2 Group NF: Nutrient- and Food-based guidelines

These recommendations begin with the instruction: '*Your dietary recommendation is to reduce your intake of free sugars to less than 5% of your total energy intake. To aid with this, reduce your intake of foods high in free sugar*'. Participants will then be provided with the same nutrient-based information as Group N plus four additional pages detailing which foods are commonly high in free sugars and examples of how much sugar is included, e.g. '*A bowl of sugary breakfast cereal could contribute 70g of sugar (up to 22 sugar cubes) to your diet over a week*'. Current recommendations from PHE (NHS 2018, 2019) have been amended to provide the nutrient- and food-based information that relates to sugars.

5.1.3 Group NFS: Nutrient-, Food- and Food-Substitution-based guidelines.

These recommendations begin with the instruction: '*Your dietary recommendation is to reduce your intake of free sugars to less than 5% of your total energy intake. To aid with this, reduce your intake of foods high in free sugar and replace these with low sugar versions*'. Participants will be provided with the same nutrient- and food-based information as Group NF, plus five additional pages on low-calorie sweeteners (LCS) and low sugar versions of foods. This information details what LCS are, where they are found, their different uses, and suggests low sugar substitutions for high sugar products, e.g. '*biscuits – swap for oatcakes, oat biscuits, or unsalted rice cakes*'. This information has been gained from Diabetes UK (Diabetes UK, 2021) and includes only details on LCS with removal of all references to diabetes.

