7 PROCEDURE

7.1 TRIAL SETTING

[figure not shown]
The trial is based in the United Kingdom and run from Bournemouth University. Recruitment started in April 2021 with testing commencing in May 2021. The trial will run for a total period of 18 months, over the year to ensure against seasonal effects, but we anticipate increased recruitment at certain times of the year (January - February and May – July). The trial will not continue over the Christmas period to avoid potential effects as a result of festive intakes.

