Three distinct analyses were pre-specified in advance: 1) Analyses of the population as a whole to investigate the effects of the three different types of dietary recommendation versus control; 2) Analyses of the effects of the dietary recommendations in different population subgroups, and 3) Investigation of the barriers and facilitators to success.

Data presentation

Data will be presented as mean \pm standard deviation in all cases, unless stated. Values will be considered significant at the $p<0.05$ level. Before completing analyses, data will be checked for normality. The data set is large, $N=242$, thus a normal distribution will be assumed. Where assumptions of homogeneity of variance are violated (Levene's test $p<0.05$), statistics will be taken from analyses conducted assuming non-equal variances. Bonferroni corrections for multiple testing will be applied to data where tests were not pre-specified in the study protocol. Where multiple regression analyses are used, all variables will be checked for multicollinearity using correlation cut-offs of <0.7 . Pearson correlation values will be used for all continuous variables, and Spearman correlations for categorical variables.

Participant characteristics

Details of study completion will be provided and a CONSORT diagram created detailing number randomized to each group, number completing the study in each group, drop out and number included in all analyses.

Characteristics will be given for the whole sample and for each trial group.

Analyses One: Quantitative Data

For analyses one, multiple regression analyses will be used. Analyses will be conducted for both primary outcomes, for key secondary outcomes - daily energy intake, sugar-sweetened food intake, LCS-sweetened food intake, body weight, waist circumference, and adverse events; and change (baseline - week 12) data for these outcomes; and for other secondary outcomes (dietary

composition, sweet food perceptions and preferences, sweet food choice, attitudes to sweet foods, attitudes towards eating behaviour, motives for food choice, knowledge and lifestyle variables, quality of life) if differences are found in the sample as a whole from baseline to week 12. This will reduce the number of exploratory tests undertaken. Differences from baseline to week 12 will be investigated by paired t-tests. Primary outcomes and outcomes associated with dietary composition will also be investigated in the same manner at weeks 1, 2, 4 and 8.

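### The non-key secondary outcomes are compared between arms only if all four arms pooled change from baseline to week 12, a screen that says nothing about arm differences and can skip effects specific to one recommendation

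*SAP*

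**What the plan says.** Under Analyses One: Quantitative Data, the SAP sorts outcomes into two groups. The arm regressions are unconditional for both primary outcomes, for the "key secondary outcomes - daily energy intake, sugar-sweetened food intake, LCS-sweetened food intake, body weight, waist circumference, and adverse events", and for change data on these.

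The other secondary outcomes are dietary composition, sweet food perceptions and preferences, sweet food choice, attitudes to sweet foods, attitudes towards eating behaviour, food-choice motives, knowledge and lifestyle, and quality of life. They are analysed by arm only "if differences are found in the sample as a whole from baseline to week 12". The test is named: "Differences from baseline to week 12 will be investigated by paired t-tests". So is the reason: "This will reduce the number of exploratory tests undertaken".

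The sample as a whole can only mean all arms pooled, control included. The SAP draws the same distinction under Participant characteristics: "Characteristics will be given for the whole sample and for each trial group".

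The protocol has no such condition. Section 8.1 plans a separate regression for each outcome, with the week-12 value predicted by trial arm and the baseline value. Section 3 states the aim that this serves: "Secondary aims will investigate how these different recommendations affect secondary outcomes".

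**The concern.** A before-after change in the pooled sample is a different quantity from a difference between randomised arms. The screen passes on anything that moves all arms together, whether or not the arms differ. It tends to fail when one arm changes and three do not, because the change is diluted fourfold, and when arms move in opposite directions, because the changes cancel.

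The trial compares three kinds of recommendation. An effect confined to one of them is among the results it was set up to detect. One example would be an effect of the material given only to group NFS (Protocol 5.1.3: "plus five additional pages on low-calorie sweeteners (LCS) and low sugar versions of foods"). For the screened outcomes, whether that randomised comparison is made at all depends on an uncontrolled before-after test.

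**Working it through.** The documents give no operating figure for this screen, so there is none to reproduce.

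**Inputs**
- N = 242 (SAP, Data presentation), so 242/4 = 60.5 per arm.
- Lower case: 60 per arm with 20% attrition (Protocol 4.2), so 60 × 0.8 = 48 per arm and 192 in all.
- Significance level 0.05 (SAP, Data presentation). Two-sided is assumed, as the SAP does not say.
- Assumption: effects are in units of the within-arm SD of change, equal across arms. The documents give no SDs for these outcomes.

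**Formulas**
- Pooled mean change = (d1 + d2 + d3 + d4)/4.
- Total SD = √(1 + variance of the four arm means). SE of pooled change = total SD/√N.
- SE of an arm-versus-control contrast = √(2/n).
- Power ≈ Φ(z − 1.96), where z = effect/SE.
- With equal arms and variances, the covariance between the pooled mean and any difference of two arm means is zero. The chance of passing the screen and then finding the contrast is therefore close to the product of the two.

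**One arm changes by 0.5 SD, the others by 0 (60.5 per arm)**
- Pooled change = 0.5/4 = 0.125.
- Variance of arm means = 0.25 × (1/4) × (3/4) = 0.047, so total SD = 1.023 and SE = 1.023/√242 = 0.066.
- z = 1.90, so the screen passes about 48% of the time.
- Contrast: SE = √(2/60.5) = 0.182, z = 2.75, power 79%.
- Both together: 0.48 × 0.79 ≈ 0.37 by the unrounded values, and 37% by simulation.
- At 48 per arm: screen about 39%, contrast 69%, both 27%.

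**One arm +0.5 SD, another −0.5 SD, two unchanged**
- Pooled change = 0, so the formula gives 5%. Simulation gives about 4%, because the spread between arms enlarges the SD used in the t-test.
- Each of those arms against control has 79% power (69% at 48 per arm).

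**All four arms drift by 0.25 SD, no arm effect**
- z = 0.25 × √242 = 3.89, so the screen passes about 97% of the time (93% at 48 per arm).
- Each contrast is then still tested at about 5%.

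**Same-direction effects with a flat control (60.5 per arm)**

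| Pattern | Screen passes | Found with screen | Found without |
|---|---|---|---|
| All three arms 0.5 SD | >99% | 78.5% | 78.5% |
| All three arms 0.3 SD | 94% | 35% | 38% |
| Two arms 0.5 SD | 97% | 76% | 79% |

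A larger effect in one arm only, 0.8 SD, passes 85% of the time (76% at 48 per arm).

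**The case against.** The best defence is that the screen touches only outcomes the SAP regards as exploratory, and that the expected pattern of effects would usually pass it. The three interventions are nested: each opens with the same instruction on free sugars, and group N's information is contained in NF and NFS (Protocol 5.1.1 to 5.1.3). Same-direction change in all three arms is a natural expectation, and the screen then costs little. The outcomes where substitution would most obviously separate the arms, sugar-sweetened and LCS-sweetened food intake, are exempt. All of this stands, and it limits the size of the problem.

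It does not justify the screen. Reducing the number of tests is a fair aim, but a criterion unrelated to arm differences removes real and null effects alike. It also does not replace multiplicity control. The SAP keeps Bonferroni for tests not pre-specified in the protocol, and Protocol 8.1 plans an analysis for every outcome, so no correction clearly applies once an outcome passes.

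A reader might infer more than the documents support:
- **That all secondary outcomes are affected.** Six are exempt.
- **That comparisons specific to one arm would usually be skipped.** At 0.5 SD in one arm it is about half the time. Only cancelling effects are nearly always skipped.
- **That the arms are expected to move in opposite directions.** Group N's quoted instruction concerns free sugars and does not mention sweet foods, and NFS repeats NF's instruction to cut high-sugar foods. Opposing effects are possible but not shown.
- **That seasonal drift is established.** The protocol runs the trial "over the year to ensure against seasonal effects", which is a precaution and not evidence of drift.
- **That skipped outcomes would be reported as showing no effect.** The SAP does not say how they will be reported.
- **That dilution is worse for laboratory-only outcomes.** A one-arm effect is divided by four whatever the sample size, and the documents give no laboratory-only number.

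**Conclusion.** The concern holds for the non-key secondary outcomes. The screen measures pooled change over time, is uninformative about arm differences, and departs from Protocol 8.1. Its cost is lost power where an effect is moderate and confined to one recommendation, or where arms move in opposing directions. For a one-arm effect of 0.5 SD, the chance of testing and finding it falls from 79% to about 37% (from 69% to about 27% at 48 per arm). Where the recommendation arms move together, the cost is small or nil.

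It might be read as a source of false positives. It is not: under equal arms and variances the screen leaves the error rate of each contrast at about 0.05, even after a shared drift. Conclusions on the primary and key secondary outcomes are untouched.

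The figures rest on a two-sided 0.05 level, equal SDs of change and contrasts of change scores. Baseline adjustment would raise the power of the contrasts but leave the screen as it is.

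**What to change.** Delete the pooled paired t-test as a condition for analysis. Run the baseline-adjusted arm model for every listed secondary outcome, as Protocol 8.1 plans. Then either label this family exploratory, or use one omnibus arm test per outcome with Holm or false-discovery-rate control across the family. Keep the pooled baseline-to-week-12 changes as description only.

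The cost is a change of SAP wording and a few more regressions on data already due to be collected. If a correction is used, the threshold for each outcome becomes stricter.

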1 ABSTRACT (250 WORDS)

Background: Dietary guidelines are intended to inform and aid the general public, with the aim of improving healthy diets and reducing health risk. The effectiveness of these guidelines however is rarely investigated.

Aim: This work investigates the effects of three different types of dietary recommendations for reducing free sugars, on free sugar intakes over 12 weeks. Secondary aims will also investigate how these different recommendations affect secondary outcomes, outcomes in subsets of the trial population, and identify barriers and facilitators to dietary change.

Methods: Using a randomised controlled parallel-group trial with three intervention and one control arm, 240 individuals consuming >5% total energy intake from free sugars will be randomized to receive: nutrient-based, nutrient- and food-based, nutrient-, food- and food-substitution-based recommendations or no recommendations, with outcomes assessed for the following 12 weeks. Our primary outcomes are free sugar intakes and adherence to the recommendations. Secondary outcomes are daily energy intake, dietary composition, anthropometry, sweet food perceptions and preferences, sweet food choice, attitudes towards sweet foods, eating behaviour, and food choice, knowledge and lifestyle variables, quality of life, adverse events, and barriers and facilitators towards intervention adherence.

Results: Data will contribute to three distinct analyses: 1) Analyses to investigate the effects of the three different dietary recommendations versus control; 2) Analyses of the effects of the dietary recommendations in different population subgroups, and 3) Investigation of the barriers and facilitators to success.

Conclusion: This work offers new perspectives on the efficacy of different dietary recommendations to enact behaviour change.

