8.1 ANALYSES ONE: EFFECTS OF THE DIFFERENT DIETARY RECOMMENDATIONS

To test the effects of the different dietary recommendations, a series of multiple regression analyses will be run. A separate analysis will be run for each outcome variable, where the outcome at week 12 will be predicted by trial arm (intervention/control) and outcome variable at baseline. Additional independent variables will also be included in each analysis as possible, to include: demographic variables, total energy intakes, sweet liker status; PROP taster status; and attitudes to sweet foods, eating behaviour and food choice.

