Primary models will include gender, age, control/intervention group, baseline %FS, baseline body weight (as randomization variables), and baseline variable of interest. In analyses for %FS, sugar-sweetened food intake, LCS-sweetened food intake, body weight and waist circumference, TEI at Week 12 and physical activity at Week 12 will also be included. Secondary models will also include any additional variable that correlates with each outcome when assessed independently. All variables measured will be considered as secondary variables. Effects for all continuous variables will be investigated using linear multiple regression. Effects for adherence will be investigated using logistic regression to predict adherent vs not adherent.

Analyses Two: Quantitative Data

For analyses two, analyses one will be repeated for demographic groups where significant associations for these variables were found in analyses one. Analyses will only be conducted if significant associations are reported. If no significant associations with demographic variables are found, these analyses will not be completed. These analyses are intended to demonstrate differing effects of the intervention/s in different population groups.

Analyses Three: Qualitative Data

Analyses three will investigate the qualitative data collected from a subset of participants using solo interviews. These interviews were scheduled for completion in a sample of 80 participants from different intervention groups and at different time points. These analyses will be undertaken using a thematic framework analysis. First, a random sample of interviews will be analysed inductively using thematic analysis to identify codes. These codes will be used to create a framework and the framework then applied to all interviews.

Framework analysis has been chosen as a suitable analytical method for evaluating the qualitative interview data gathered, due to an interest in individual experiences and seeks to identify the different factors (barriers or facilitators) that contributed to successful or unsuccessful dietary change (Braun & Clark, 2013). The practical methods for conducting framework analysis follow a methodology as outlined below.

Framework analysis (Braun & Clarke, 2006; 2013; Gale et al, 2013).

Phase 1 'Familiarizing yourself: Transcribing data (if necessary), reading and re-reading the data, noting down with your data: initial ideas'.

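### The arm term is written with two levels only, and no comparison between the three recommendation types is planned

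*SAP*

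**What the plan says.** **Aim and design.** Protocol section 3 describes a "randomised controlled parallel-group trial with three intervention arms and one control arm" and states: "The primary purpose is to assess the effects of three different types of dietary recommendations for reducing free sugars". Sections 5.1.1 to 5.1.3 build the arms cumulatively. NF receives everything in N plus pages on foods, and NFS receives everything in NF plus pages on sweeteners and low-sugar swaps. The SAP (Data Analysis, Outcomes) gives the purpose of the first analysis as to "investigate the effects of the three different types of dietary recommendation versus control". Protocol section 8 says much the same.

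**Model.** In Protocol section 8.1, "the outcome at week 12 will be predicted by trial arm (intervention/control) and outcome variable at baseline". In the SAP, Analyses One, "Primary models will include gender, age, control/intervention group, baseline %FS, baseline body weight". Continuous outcomes go into linear regression and adherence into logistic regression.

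**What is not stated.** Neither document gives the number of levels of the arm term, its coding, a reference arm, an overall test of arm, or any quantitative contrast between two recommendation types. The SAP's other mentions of groups concern participant characteristics and the interpretation of the interviews.

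**Multiplicity.** SAP, Data presentation: "Bonferroni corrections for multiple testing will be applied to data where tests were not pre-specified in the study protocol".

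**The concern.** The only wording that defines the arm term names two categories, while the aim needs an estimate for each of three types. An analyst who followed the text literally would fit a single advice-versus-control coefficient. That coefficient says whether advice works on average. It does not say whether nutrient information alone works, or what the food pages and the substitution pages add.

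The second gap remains even if four levels were meant. Three effects versus control do not by themselves show whether two types differ. Without planned contrasts, a report could slide into noting that one type reached p<0.05 and another did not, which is not a test of the difference between them. The Protocol abstract closes with the claim "This work offers new perspectives on the efficacy of different dietary recommendations to enact behaviour change", which invites such comparisons.

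**Working it through.** The plan gives no figure for this point, so the check has three parts: what each reading of the model estimates, why versus-control p-values do not compare types, and what power a contrast between types would have. All effect sizes below are assumptions for illustration.

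**Inputs (Protocol section 4.2).** Target difference 2 percentage points; standardised difference 0.8; alpha 0.05 (taken as two-sided); 60 per arm; 20% attrition. Hence SD = 2/0.8 = 2.5 points, and completers per arm = 60 × 0.8 = 48. The SD comes from a saturated-fat trial and may not carry over.

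These inputs do not reproduce 60 per arm. n = 2(1.96 + 0.84)²/0.8² gives 25 per arm, and 25/0.8 gives 32 after attrition. That is a separate matter and does not affect this point.

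**1. What a two-level term estimates.** With three equal advice arms, the coefficient is (effect of N + effect of NF + effect of NFS)/3.

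| Assumed true reductions vs control (N, NF, NFS) | Two-level estimate |
|---|---|
| 1, 1, 1 | 1.0 |
| 0, 1, 2 | 1.0 |
| 0, 0, 3 | 1.0 |

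Three different answers to the trial's question give the same result. In the second row the estimate misses both N and NFS by 1 point, half of the 2-point design difference.

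**2. Why versus-control p-values do not compare types.** With 60 per arm, SE = 2.5 × √(2/60) = 0.456. Suppose N shows 0.7 points and NF 1.0 point versus control.
- N: 0.7/0.456 = 1.53, p = 0.13.
- NF: 1.0/0.456 = 2.19, p = 0.03.
- NF minus N: 0.3 ± 1.96 × 0.456, a 95% CI of about -0.6 to 1.2.

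One type is significant and the other is not, yet there is no evidence that they differ. The split depends on the numbers chosen: with 48 per arm, SE = 2.5 × √(2/48) = 0.51, and 1.0/0.51 = 1.96, so p is about 0.05. The example shows the logic and does not predict this trial's results.

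**3. Power of a contrast between two types.** With 48 completers per arm, power ≈ Φ(gap/0.51 − z), where z is the two-sided critical value.

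| True gap (points) | alpha 0.05 | 0.05/3 | 0.05/6 |
|---|---|---|---|
| 1.0 | 50% | 33% | 25% |
| 1.25 | 69% | 52% | 43% |
| 1.5 | 84% | 71% | 62% |
| 2.0 | 97.5% | 94% | 90% |

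The gap detectable with 80% power is 1.43, 1.65 and 1.78 points respectively. Division by 3 corresponds to three contrasts on one outcome, and division by 6 to three contrasts on both primary outcomes. Baseline adjustment would reduce the SE somewhat; the documents give no correlation from which to calculate by how much.

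**The case against.** The strongest reply is that the wording is loose and the intention clear. Protocol sections 4.2, 4.3 and 5 use trial arm for one of four arms, so the bracketed gloss in section 8.1 may only distinguish the advice arms from control. Both documents define the first analysis as three types versus control, and neither says that the arms will be pooled. This stands. A reader might infer that the sponsor plans to pool the advice arms, or that the trial cannot separate the recommendation types. The documents do not support either inference: pooling is nowhere stated, and the randomised data can give every arm-specific effect and pairwise difference once the model is written with four levels.

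A second reply is that the stated comparison is with control only, which is a legitimate design. This also stands. Contrasts between types are a recommendation drawn from the cumulative arms, not a stated aim that the plan fails to meet. A reader might also infer that the recommendations will be ranked by which reach p<0.05. Neither document says so; the risk comes from leaving the comparison unplanned.

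These replies do not remove the ambiguity. The two readings give different models, and the SAP does not choose between them.

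**Conclusion.** The point holds as a gap in specification. Taken literally, the arm term in both documents gives one averaged effect and does not deliver the stated aim of three effects versus control. Read generously as a four-level factor, it does deliver that aim, but the factor and its reference arm are unstated. On either reading, no comparison between types is planned.

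The size depends on how far the true effects differ. If all three types work equally well, the averaged effect is right for each. With assumed effects of 0, 1 and 2 points, it is wrong by 1 point for two of the three types. The specification gap itself does not depend on the sample size or on the SD of 2.5; the power figures do.

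**What to change.** 1. In Protocol section 8.1 and SAP Analyses One, replace the intervention/control wording with three indicator terms (N, NF, NFS), control as reference. Apply this to every Analyses One model, including the logistic model for adherence.
2. From the same models, report NF-N, NFS-NF and NFS-N with confidence intervals for the primary outcomes. Base any statement that one type is better than another on these contrasts, not on which arms reach p<0.05 versus control.
3. The contrasts are not in the protocol, so the SAP's Bonferroni rule applies to them. State the number of tests (three contrasts on two primary outcomes at week 12 make six) and label the contrasts as added in the SAP. The SAP reports that the main researcher was blinded during data handling and imputation. If group labels are still masked, make the change before they are revealed; if not, say so.
4. If only versus-control results are wanted, step 1 is still needed, and the SAP should say that no claims comparing types will be made.

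**Cost.** A change of wording and three contrasts per primary outcome, with no new data. Power is limited for small gaps, so the confidence intervals should carry the interpretation, and a non-significant contrast should not be read as equivalence.
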